5.2. Statistical Analysis

All data will be collected by the site and entered into a database. Subjects will be assigned an ID number. Data analysis will be performed without patient identification. Statistical analysis will be performed using standard descriptive statistics and other tests as deemed appropriate based on the characteristics of the data to be analyzed. All statistical tests will be two-sided and interpreted at a 5% significance level. Comparisons between the groups will be made. Data analysis will be conducted by a third party consultant.

5.3. Study Endpoints:

Comparisons between the groups:

1. Primary Endpoints:

- Binocular distance-corrected near (40 cm) visual acuity.

- Reduction of astigmatism.

2. Secondary Endpoints:

- Uncorrected and distance-corrected near (40 cm) visual acuity at 1 month and 3 months
- Uncorrected and distance-corrected intermediate (66 cm) visual acuity at 1 month and 3 months
- Uncorrected and best-corrected distance (4 m) visual acuity at 1 month and 3 months
- To evaluate patient's overall satisfaction of their vision
- To evaluate patient's spectacle independence
- To evaluate visual symptoms using a questionnaire.
- Residual mean spherical equivalent refraction at 1 and 3 months
- Residual refractive sphere at 1 month and 3 months
- Residual refractive cylinder at 1 month and 3 months
- Percentage of eyes with postoperative MRSE accuracy to target $\leq 0.5\text{D}$ at 1 and 3 months
- Determine stability of toric iol from time of surgery to 3 months postoperative
- To evaluate the surgeons experience and overall satisfaction

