3.4. Measurements and evaluations

1. Visit 1: Informed consent process will be conducted at this visit. Assessments include uncorrected and best-corrected ETDRS visual acuity at 4 m (UCVA / BCVA), manifest refraction, intraocular pressure (IOP) using Goldman tonometer, corneal topography, undilated photopic and mesopic pupil size, slit lamp examination including dilated fundus exam, cataract density and type, and HD analyzer. Any testing that is part of the site's standard of care preoperative cataract surgery evaluation may be performed prior to the informed consent being signed provided these tests are conducted within 90 days of the surgery and notation of the date performed is entered onto the CRF. The surgeon's standard pre cataract surgery treatment will be used in all his patients

Each subject will be randomized to Group A or B. Randomization will ensure that an equal number of subjects are enrolled in each group.

2. Visit 2: The surgeon may use his preferred cataract extraction technique (manual or laser). The lens will be implanted in the bag. The following information will be captured the day of surgery: phaco technique (manual or laser), lens implanted and power, target refraction for

IOL power implanted, additional surgical procedures, intraoperative complications, and any device deficiencies. The surgeon's standard post cataract surgery treatment will be used in all his patients. IOL power changes based on intraoperative aberrometry (i.e. ORA) are not allowed but it can be used to align the lens.

3. Visit 3: monocular UCVA, slit lamp examination, IOP, and lens orientation (measured using slit lamp photography).
4. Visit 4: Slit lamp examination, manifest refraction, UCVA, BCVA, UCIVA (at 66 cm), DCIVA (at 66 cm), UCNVA (at 40 cm), DCNVA (at 40), and UCNVA at best distance, undilated photopic and mesopic pupil size, IOP, IOL orientation (measured using slit lamp photography), dilated fundus exam (as deemed necessary by the investigator), patient satisfaction, visual symptoms and spectacle independence questionnaires, HD Analyzer, and any device deficiencies.

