5. Visit 5: Slit lamp examination, manifest refraction, UCVA, BCVA, UCIVA (at 66 cm), DCIVA (at 66 cm), UCNVA (at 40 cm) and DCNVA (at 40), and UCNVA at best distance, undilated photopic and mesopic pupil size, IOP, IOL orientation (measured using slit lamp photography), reading speed, defocus curve, dilated fundus exam (as deemed necessary by the investigator), patient satisfaction, visual symptoms and spectacle independence questionnaires, HD Analyzer, keratometry measurement with the device used to calculate the toric power, and any device deficiencies.

All adverse events and complaints will be monitored and recorded at all study visits.

Table 1. Visits and Study Assessments

	Visit 1 Screening	Visit 2 DOS	Visit 3 POD #1	Visit 4 1-Month	Visit 5 3-Month
Informed Consent	X				
Inclusion/Exclusion	X				
Demographics/PMH/Ocular history	X				
UCVA ETDRS (4m)	X		X	X*	X**
Manifest refraction – Max Plus	X			X	X
BCVA ETDRS (4m)	X			X*	X**
UCIVA ETDRS (66 cm)				X*	X**
DCIVA ETDRS (66 cm)				X*	X**
UCNVA ETDRS (40 cm)				X*	X**
DCNVA ETDRS (40 cm)				X*	X**
UCNVA at best distance				X*	X**
Reading speed					X**
Defocus curve					X**

Intraocular Pressure (Goldman)	X		X	X	X
SLE	X		X	X	X
Dilated fundus exam	X			X†	X†
Cataract density / type	X				
Corneal topography	X				
Undilated photopic and mesopic pupil size	X			X	X
Intraop data		X			
Toric IOL position		X	X	X	X
Questionnaires				X	X
HD Analyzer	X			X	X
keratometry measurement with the device used to calculate the toric power					X
AE/Device deficiencies		X	X	X	X

X To be performed as scheduled

* Monocular and binocular testing

** Binocular testing only

† To be performed as deemed necessary by the investigator.

4. Study endpoint criteria

4.1. Patient Completion of Study: If a study patient has completed the final visit (Visit 5) of the study, he/she is considered to have completed the study.

4.2. Patient Discontinuation: Each study patient may voluntarily discontinue the study at any time they choose. Study patients who cannot complete the study for administrative reasons (e.g., non-compliance, failure to meet visit schedule, etc.) will be discontinued from the study. Study patients discontinued during the enrollment phase (prior to surgery) of the study will be replaced.

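### Two between-group primary endpoints have no visit and no success rule, and every test is at an unadjusted 5%; if either one can carry the trial, the primary false-positive risk is about 8% to 10%

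*Combined protocol and SAP*

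**What the plan says.** Section 5.3 places all its endpoints under a between-group heading. The primary list has two entries, "Binocular distance-corrected near (40 cm) visual acuity" and "Reduction of astigmatism". Neither names a visit. The astigmatism entry also gives no measure, baseline reference or eye.

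The secondary list is more specific. All seven of its acuity and refraction items name 1 and 3 months, among them "Uncorrected and distance-corrected near (40 cm) visual acuity at 1 month and 3 months" and "Residual refractive cylinder at 1 month and 3 months".

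Section 3.4 schedules the underlying measurements at both postoperative visits. The Month 1 entry begins "Visit 4: Slit lamp examination, manifest refraction" and the Month 3 entry begins "Visit 5: Slit lamp examination, manifest refraction". Both entries, and Table 1, include distance-corrected near acuity at 40 cm.

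On significance, section 5.2 says only: "All statistical tests will be two-sided and interpreted at a 5% significance level". No section available for review gives a hierarchy, an alpha split, a co-primary rule or any other multiplicity control. Section 5.1 sizes the trial on near visual acuity alone, with a two-sided t-test at alpha 0.05.

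**The concern.** A reader cannot tell from the plan which result would make the trial positive. With two primary endpoints, a per-test level of 5% fixes the overall error only once the success rule is known. If either endpoint suffices, two chances at 5% give an overall risk above 5%. If both are required, the error is held, but power becomes a joint quantity that the plan does not address.

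The astigmatism endpoint makes this a practical matter. Both groups receive the same toric lens and differ only in the refractive target of the non-dominant eye (sections 2.1 and 3.2). The plan states no expected between-group difference in astigmatism. A significant result on that endpoint alone could therefore well be chance, and nothing in the plan prevents it from being presented as a primary success.

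The missing visit adds a smaller freedom of the same kind, because both measures are taken at Month 1 and at Month 3.

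**Working it through.** **Inputs from the plan.** Two-sided 5% for every test (section 5.2). SD 0.16 logMAR, difference 0.1 logMAR, 90% power, 55 per group, 60 per group enrolled (section 5.1). The documents give no correlation between endpoints or between visits, so every correlation below is an assumption.

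**Step 1: the plan's own figure.** The normal approximation is n = 2(1.960 + 1.282)² × 0.16² / 0.1² = 2 × 10.51 × 2.56 ≈ 53.8, so 54 per group. The exact noncentral t calculation (standardised difference 0.1/0.16 = 0.625) gives 89.6% power at 54 and 90.1% at 55. The stated 55 per group reproduces.

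**Step 2: either endpoint counts, one fixed visit.** With no true difference on either endpoint, the risk is 1 − P(|Z₁| < 1.96 and |Z₂| < 1.96) for a bivariate normal pair with correlation r. At r = 0 this is 1 − 0.95² = 0.0975.

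| Assumed endpoint correlation | False-positive risk | Simulated t-tests, 55 per group (100,000 runs) |
|---|---|---|
| 0 | 9.75% | 9.79% |
| 0.5 | 9.07% | 9.06% |
| 0.8 | 7.81% | 7.86% |

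Relative to 5%, this is a factor of 1.6 (7.81/5) to 2.0 (9.75/5).

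**Step 3: both must succeed, one fixed visit.** A false claim requires at least one truly null endpoint to reach significance, so the risk is at most 5%. Joint power cannot exceed the smaller of the two single-endpoint powers. The plan gives 90% for near acuity and nothing for astigmatism, so no joint power can be calculated. If there is no true astigmatism difference between the groups, the chance of joint success is at most 5%.

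**Step 4: fixed sequence, near acuity first.** If near acuity is truly null, any false primary claim must first pass its 5% test. If it is not null, only the 5% astigmatism test can give a false claim. The overall risk is at most 5% either way, and near acuity keeps its full alpha.

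**Step 5: equal alpha split, 0.025 each.** The overall risk is at most 5% (1 − 0.975² = 4.94% if independent). Near-acuity power under the plan's SD and difference:

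| Analysed per group | Alpha 0.05 | Alpha 0.025 | Loss |
|---|---|---|---|
| 55 | 90.1% | 84.1% | 6.0 points |
| 60 | 92.4% | 87.4% | 5.0 points |

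At 0.025, 65 per group would be needed for 90% (64 gives 89.6%, 65 gives 90.1%).

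**Side note on visit choice.** Suppose that either endpoint counts and also that the visit is picked after the data are seen. One endpoint tested at two visits carries a risk p of 7.04%, 8.35% or 9.07% for a between-visit correlation of 0.9, 0.7 or 0.5. Two independent endpoints then give 1 − (1 − p)² = 13.6%, 16.0% or 17.3%. These figures stack a second hypothetical on the first and do not carry the conclusion.

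**The case against.** The strongest reply is that the inflation belongs to a reading the plan never states. The objective is to evaluate visual outcomes, no success criterion is declared, and no section describes a regulatory or labelling claim. Section 5.1 sizes the trial on near acuity at the full alpha of 0.05, which suggests that near acuity leads. If it leads, or if both endpoints must succeed, the error at one fixed visit is 5%. This much stands: the 8% to 10% is conditional. But a sample-size basis is a hint and not a success rule. It also does not clearly identify the listed primary, because section 5.1 ties its SD to logMAR UCVA while the primary in section 5.3 is distance-corrected.

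A reader might go further and infer that the trial will run at a 14% to 17% error rate because the visit is open. The documents do not support that. Distance-corrected near acuity and residual cylinder are secondary endpoints at both months, so both visits are due to be reported and a selective choice would be visible. Visibility does not control the error, but it makes the visit question secondary.

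The case against also bears on the remedy. Distance correction removes the intended −0.50 D offset, so a 0.1 logMAR difference on the listed primary is doubtful, and a sequence led by that endpoint might never reach astigmatism. This stands, and it makes the testing order conditional.

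Finally, removing duplicated secondary items or labelling secondary p-values as nominal would be a reporting preference and is not needed to control the primary error.

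**Conclusion.** The gap is real and should be fixed. The plan has two between-group primary endpoints, no primary visit, no success rule and no multiplicity control. Under an either-endpoint reading, the primary false-positive risk at one fixed visit is about 8% to 10%, for assumed endpoint correlations from 0.8 down to 0. Under a both-must-succeed reading the error is held at 5%, but the stated 90% power describes only one of the two endpoints.

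The documents do not support saying that the trial's error rate simply is 8% to 10%, because they neither adopt nor exclude the reading that produces it. The power figures assume the plan's SD of 0.16 and difference of 0.1 and carry over to distance-corrected near acuity only if those values apply to it.

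**What to change.** Before any between-group look at the data, amend sections 5.2 and 5.3 as follows.

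1. Name one primary visit, for example Month 3, which is the final visit.
2. Define reduction of astigmatism: the measure, the baseline it is taken from, and the eye or eyes analysed.
3. Settle which near-acuity variable is primary, so that it matches the variable behind the SD in section 5.1.
4. Then specify a fixed sequence at two-sided 0.05, with near acuity first and astigmatism tested only if near acuity is significant. Making astigmatism a secondary endpoint is an equally acceptable route.

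An equal split of alpha is a workable alternative if the sponsor wants astigmatism to stand independently. Its price is the 5 to 6 points of near-acuity power shown above.

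The amendment adds no subjects, visits or measurements. What is given up is that a significant result on astigmatism alone, or at the visit not named as primary, could not be claimed as a primary success.

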2.1. Test article: Toric Tecnis Symfony IOL (ZXT) (Abbott Medical Optics)

2.2. Study Design: Prospective, multicenter (up to 4 sites in USA), randomized, bilateral eye study.

2.3. Subjects:

1. Inclusion Criteria:

Subjects MUST fulfill the following conditions to qualify for enrollment into the trial

1. Subject is undergoing bilateral cataract extraction with intraocular lens implantation.
2. Gender: Males and Females.
3. Age: 40 years and older.
4. Willing and able to provide written informed consent for participation in the study
5. Willing and able to comply with scheduled visits and other study procedures.
6. Scheduled to undergo standard cataract surgery with topical anesthesia in both eyes within 6-15 days between surgeries.

7. Subjects who require an IOL power in the range of +5.0 D to +34.0 D only.
8. Potential postoperative visual acuity of 0.2 logMAR (20/32 Snellen) or better in both eyes.

2. Exclusion Criteria:

Subjects with ANY of the following conditions on the eligibility exam may NOT be enrolled into the trial.

1. Severe preoperative ocular pathology: amblyopia, rubella cataract, proliferative diabetic retinopathy, shallow anterior chamber, macular edema, retinal detachment, aniridia or iris atrophy, uveitis, history of iritis, iris neovascularization, medically uncontrolled glaucoma, microphthalmos or macophthalmos, optic nerve atrophy, macular degeneration (with anticipated best postoperative visual acuity less than 20/30), advanced glaucomatous damage, etc.
2. Uncontrolled diabetes.
3. Use of any systemic or topical drug known to interfere with visual performance.
4. Contact lens use during the active treatment portion of the trial.
5. Any concurrent infectious/non-infectious conjunctivitis, keratitis or uveitis.
6. Clinically significant corneal dystrophy
7. History of chronic intraocular inflammation.
8. History of retinal detachment.
9. Pseudoexfoliation syndrome or any other condition that has the potential to weaken the zonules.
10. Previous intraocular surgery.
11. Previous refractive surgery.
12. Previous keratoplasty
13. Severe dry eye
14. Pupil abnormalities
15. Subject who may reasonably be expected to require a secondary surgical intervention at any time during the study (other than YAG capsulotomy, i.e. LASIK)
16. Anesthesia other than topical anesthesia (i.e. retrobulbar, general, etc).

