3.1. Informed Consent / Subject enrollment

Potential subjects will be identified from the patients presenting at the clinic. Additionally, an ad will be placed in the local newspaper and in the practice website. Once identified as a study candidate, the patient will be asked if he/she would like to participate. The sub-investigator, study coordinator or an appropriately trained staff member will answer any and all questions and will obtain informed consent. A copy of the signed informed consent document will be given to the subject. The principal investigator will be available if the subject wants to discuss further details with him. Any testing that is part of the investigative site's standard preoperative cataract evaluation may be performed prior to the informed consent being signed, provided these tests are conducted within 90 days of surgery. The patient will

understand that participation in the study, or declining to participate, will not affect his/her quality of care.

No subject will be enrolled into the study that does not meet the inclusion/exclusion criteria and does not sign the current approved informed consent document. Informed consent will be obtained prior to collecting any data for the study. The original signed documents will be maintained by the investigator as a permanent part of the subject's research records and a scanned copy will be uploaded to the subject's electronic medical record.

3.2. Surgery Procedures:

Patients will be randomized to one of two groups:

- Group A, plano OU. The target refraction for both eyes will be emmetropia (± 0.25 D).
- Group B, nano-vision. The target refraction for the dominant eye will be plano and for the non-dominant eye -0.50 ± 0.16 D.

3.3. Study Visit Schedule and Assessments (Table 1).

1. Visit Schedule: Subjects will be examined at the following intervals:

1. Visit 1: Screening and enrollment: Preoperative evaluation completed not more than eight weeks before surgery
2. Visit 2: Day of Surgery
3. Visit 3: Day 1: (12 to 48 hours) after surgery
3. Visit 4: Month 1: 30 ± 5 days postoperative after second eye surgery
4. Visit 5: Month 3: 90 ± 15 days postoperative after second eye surgery

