5. STATISTICAL CONSIDERATIONS

5.1. Sample size

The sample size estimates depend in large part on the standard deviation (SD) for logMAR UCVA. Assuming a SD of 0.16 (mean from previous Symfony studies)), for the two-sided t-test (alpha =0.05) for the near visual acuity endpoint, we will need 55 subjects in each group (emmetropia / nano-vision) to detect differences of 0.1 logMAR with 90% power. Total sample size = 110. Allowing 10 % for the potential confounding factor of having 4 sites, 120 subjects will be enrolled (60 in each group). Table 2 summarizes the sample size estimate.

Table 2. Sample size estimate.

	Toric Group	
	Emmetropia	Nano-Vision
Sample size	55	55
5% multiple sites	5	5
Total sample size	60	60

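### The sample size is justified with an SD for uncorrected acuity, but the primary acuity endpoint is distance-corrected near acuity, where the randomised -0.50 D offset is neutralised and 0.1 logMAR has no stated basis

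*Combined protocol and SAP*

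**What the plan says.** Section 5.1 opens with "The sample size estimates depend in large part on the standard deviation (SD) for logMAR UCVA". It assumes an SD of 0.16, attributed without citation to earlier studies of the lens. Using a two-sided t-test at alpha 0.05 "for the near visual acuity endpoint", it asks for 55 subjects per group "to detect differences of 0.1 logMAR with 90% power", raised to 60 per group as an allowance for multiple sites. It does not say whether the near measure is uncorrected or distance-corrected.

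Section 5.3 lists two primary endpoints: "Binocular distance-corrected near (40 cm) visual acuity", with no visit named, and reduction of astigmatism. The secondary list includes "Uncorrected and distance-corrected near (40 cm) visual acuity at 1 month and 3 months", so distance-corrected near acuity appears in both lists and uncorrected near acuity only in the second. Also secondary is "To evaluate patient's spectacle independence".

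Section 2.1 gives a single test article, the toric Symfony lens. Under section 3.2 the randomised groups differ only in the target for the non-dominant eye: plano in Group A, -0.50 D in Group B. Table 1 schedules uncorrected (UCNVA) and distance-corrected (DCNVA) near acuity at 40 cm as separate tests, both done binocularly at Months 1 and 3.

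**The concern.** The introduction gives the reason for the trial: this type of lens may be weaker at near than a multifocal, and a small residual myopia in the non-dominant eye is one way to offset that. The documents do not define distance correction. On its ordinary meaning, the subject reads the near chart through the correction that makes distance vision sharp, and that correction cancels the -0.50 D. The primary acuity test would then remove the randomised contrast before measuring its effect.

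The measures on which the offset can act are uncorrected near acuity at 40 cm, uncorrected near acuity at best distance, uncorrected intermediate acuity and spectacle independence. None is primary, and near acuity at best distance is measured but does not appear among the section 5.3 endpoints at all.

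The stake is interpretation. A null result on the primary acuity endpoint is what one would expect whether or not nano-vision helps at near, yet a reader could take it as evidence of no near benefit from a trial said to have 90% power. The outcomes that could show a benefit carry no power statement.

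**Working it through.** **Inputs from section 5.1:** two-sided alpha 0.05, SD σ = 0.16, difference δ = 0.1 logMAR, n = 55 per group (60 enrolled per group). The documents give no SD and no expected difference for distance-corrected near acuity. A residual difference of 0.05 logMAR and an SD of 0.18 are used below as assumptions, to show sensitivity.

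**Method.** Two-sample t-test. Power = P(|T| > t(0.975; 2n − 2)), where T is noncentral t with 2n − 2 degrees of freedom and noncentrality λ = δ / (σ√(2/n)).

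**1. The plan's own figure.** The normal approximation gives n = 2(1.960 + 1.282)² × 0.16² / 0.1² = 53.8, so 54. The exact t calculation gives 54.8, so 55, as stated. At n = 55, λ = 0.1 / (0.16 × √(2/55)) = 0.1 / 0.0305 = 3.28 and power is 90.1%. At n = 60, λ = 3.42 and power is 92.4%.

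**2. Distance-corrected near acuity, SD 0.16.** With δ = 0, λ = 0 and the chance of a significant result is alpha, 5%, at any n. With δ = 0.05 at n = 55, λ = 0.05 / 0.0305 = 1.64.

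**3. Uncorrected near acuity.** The figures in step 1 apply only if SD 0.16 and δ = 0.1 both hold for the binocular uncorrected measure, which the documents do not show. With σ = 0.18 at n = 55, λ = 0.1 / (0.18 × √(2/55)) = 0.1 / 0.0343 = 2.91.

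| Scenario | Power, 55 per group | Power, 60 per group | n per group for 90% |
|---|---|---|---|
| δ 0.10, σ 0.16 (plan) | 90.1% | 92.4% | 55 |
| δ 0, σ 0.16 | 5.0% | 5.0% | none |
| δ 0.05 (assumed), σ 0.16 | 36.9% | 39.7% | 217 |
| δ 0.10, σ 0.18 (assumed) | 82.3% | 85.5% | 70 |

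At 60 analysed per group, 90% power for 0.1 logMAR holds up to an SD of about 0.168. Both 55 and 60 are shown because 55 is the powered number and section 2.3 removes subjects with aborted surgery from the efficacy analysis.

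**4. Precision.** The 95% CI half-width for a between-group difference at SD 0.16 is t × σ√(2/n): 1.98 × 0.0305 = 0.060 logMAR at 55 per group and 1.98 × 0.0292 = 0.058 at 60.

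**The case against.** The strongest reply is that power is conditional. Section 5.1 states a detectable difference, not a forecast. If the SD of distance-corrected near acuity is 0.16, then 90% power for 0.1 logMAR is correct whatever the true difference is. With a half-width of 0.060, an observed difference near zero would exclude 0.1 logMAR, which is informative. This stands as far as it goes. But section 5.1 takes its SD from another measure, the plan frames the test as detecting a difference, and no section states an equivalence aim or margin.

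The objective is also broad: it concerns visual outcomes in general and sets no near-acuity hypothesis. The uncorrected outcomes are collected and, apart from near acuity at best distance, are listed for comparison. This too stands. The sponsor may choose the primary measure, and what is lost is endpoint status and a power statement rather than data. It does not excuse powering one measure and naming another.

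Several cautions about the numbers are fair:

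- The direction of any SD error for the distance-corrected measure is unknown. A smaller SD would raise power at a fixed difference, though it cannot help if the difference is zero.
- Section 3.4 and Table 1 use UCVA for acuity at 4 m, so 0.16 may not be a near-acuity SD at all. The introduction uses the term more loosely, so this is uncertain.
- Uncorrected near acuity is not guaranteed to show 0.1 logMAR either. One eye is shifted and testing is binocular. Under the section 3.2 tolerances, non-dominant targets could be as close as -0.25 D and -0.34 D, a gap of 0.09 D.
- The calculation gives acuity the full 0.05 although there is a second primary endpoint. With an equal split of alpha (an assumption), power for 0.1 logMAR at SD 0.16 would be 84.1% at 55 and 87.4% at 60 per group.

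These limit what can be promised for either measure. None of them ties the section 5.1 assumptions to the section 5.3 endpoint.

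**Conclusion.** The concern holds and must be fixed. Sections 5.1 and 5.3 do not describe the same variable, and 0.1 logMAR has no stated support on the one named as primary. The 90% figure applies to the primary acuity endpoint only if distance-corrected near acuity has an SD of about 0.16 and differs by 0.1 logMAR between two arms with the same lens. If correction fully neutralises the offset, as the ordinary meaning implies, the test has only its 5% false-positive rate. The case for a near-zero expected difference rests on that meaning, since the documents do not define the term. The mismatch between the sections stands under any definition.

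**What to change.** In section 5.3, make binocular uncorrected near acuity at 40 cm the primary acuity endpoint at one named visit, Month 1 or Month 3. Keep binocular distance-corrected near acuity as secondary only, reported with its between-group 95% CI, as a check that near performance is similar once the refractive target is removed. In section 5.1, name binocular uncorrected near acuity as the measure being powered, and either confirm with a source that SD 0.16 and 0.1 logMAR apply to it or restate the power.

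If the sponsor prefers to keep distance-corrected near acuity as primary, section 5.1 must name it, justify an expected between-arm difference and an SD for it, and restate the power.

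The cost is text in two sections. Table 1 already schedules the binocular uncorrected test at both visits, so no visit or test is added. The downside is that the SD and difference must be justified afresh and the stated power may fall. At an assumed SD of 0.18, for example, it would be 85.5% at 60 per group, and 90% would need 70 per group. Any change of primary endpoint should be made and dated before outcome data are seen. The documents do not show how far the trial has progressed.

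### The astigmatism primary endpoint reads as a change from the preoperative value, but no adjustment for Visit 1 cylinder is specified; an unadjusted change would be valid but less precise than the data allow

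*Combined protocol and SAP*

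**What the plan says.** Section 5.3, under "Comparisons between the groups", gives two primary endpoints: binocular distance-corrected near acuity and "Reduction of astigmatism". The second has no formula, visit, measure or unit (eye or subject). Residual refractive cylinder at 1 and 3 months, a postoperative-only measure, is listed separately among the secondary endpoints.

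On method, section 5.2 says: "Statistical analysis will be performed using standard descriptive statistics and other tests as deemed appropriate based on the characteristics of the data to be analyzed". It adds "All statistical tests will be two-sided and interpreted at a 5% significance level" and "Comparisons between the groups will be made". No model or covariate is named. The only SD in the plan is for logMAR acuity (section 5.1: "Assuming a SD of 0.16 (mean from previous Symfony studies"); there is none for cylinder.

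On data, section 3.4 lists for Visit 1 "manifest refraction, intraocular pressure (IOP) using Goldman tonometer, corneal topography". Table 1 has the row "Manifest refraction – Max Plus" marked at Visit 1, Month 1 and Month 3.

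On allocation, sections 3.4 and 8.3 describe equal group sizes and sequentially numbered envelopes supplied to each site. Neither states stratification by cylinder. Section 2.3 sets no numerical limit on preoperative cylinder.

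**The concern.** A toric lens is meant to remove the cylinder that the eye starts with. To the extent that it succeeds, the reduction is the preoperative cylinder minus a smaller residual, so eyes with more cylinder show larger reductions whichever group they are in. An unadjusted comparison of reductions then carries preoperative spread as noise. A chance difference between the groups in starting cylinder also passes, in part or in full, into the estimated group difference.

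Both groups receive the same toric lens and differ only in the refractive target of the non-dominant eye. The most useful result from this comparison is therefore a narrow interval for the effect of the nano-vision target on cylinder correction. An unadjusted change would give a wider interval than the data can support, for a primary endpoint whose natural covariate is already collected.

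**Working it through.** **The plan's own figure.** Section 5.1 uses SD 0.16, difference 0.1 logMAR, two-sided alpha 0.05 and 90% power. The normal approximation gives n = 2 × (1.960 + 1.282)² × (0.16/0.1)² = 53.8, so 54 per group. The noncentral t gives 55 (power 0.901 at 55, 0.896 at 54), so the stated 55 reproduces. It concerns near acuity only and says nothing about the precision of the astigmatism comparison.

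**Inputs for astigmatism.** From the plan: 60 per group and two-sided alpha 0.05. Assumed, because the documents give no value: baseline SD s0 = 0.50-1.00 D, Month 3 SD s1 = 0.40-0.50 D, baseline/Month 3 correlation ρ = 0-0.5, and one value per subject. The 0.25 D difference used for power is illustrative; the plan states no effect size for cylinder.

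**Formulas.**
- Variance of raw change: s0² + s1² − 2ρ·s0·s1
- Residual variance with baseline as covariate: s1²(1 − ρ²)
- Difference between the two: (s0 − ρ·s1)², which cannot be negative. As a fraction of the raw-change variance it is both the proportional cut and the share of the change explained by baseline.
- Share of a baseline imbalance passed into the raw group difference: 1 − ρ·s1/s0
- Shift from a one-standard-error baseline imbalance: (s0 − ρ·s1) × √(2/60), where √(2/60) = 0.1826
- 95% CI half-width: 1.980 × SD × 0.1826; power from the noncentral t

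**Middle case** (s0 = 0.75, s1 = 0.40, ρ = 0.3).
- Raw variance: 0.5625 + 0.1600 − 0.1800 = 0.5425 (SD 0.74 D).
- Adjusted variance: 0.1600 × 0.91 = 0.1456 (SD 0.38 D), a cut of 73%.
- The half-width falls from 0.27 to 0.14 D, and power for 0.25 D rises from 45% to 95%.
- One-standard-error shift: 0.63 × 0.1826 = 0.12 D.

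**Ends of the assumed range.**

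| s0, s1, ρ | Raw variance | Adjusted variance | Cut | Power for 0.25 D, raw to adjusted | Passed through | One-SE shift |
|---|---|---|---|---|---|---|
| 0.50, 0.50, 0.5 | 0.2500 | 0.1875 | 25% | 78% to 88% | 0.50 | 0.05 D |
| 1.00, 0.40, 0 | 1.1600 | 0.1600 | 86% | 24% to 92% | 1.00 | 0.18 D |

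**Type I error.** In 20,000 simulated trials with s0 = 0.75, s1 = 0.40, ρ = 0.2 and no group effect, the unadjusted t-test on change rejected in 4.9%. The cost is precision, plus conditional bias when baseline happens to be unbalanced. The overall false-positive rate is not inflated.

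**Equivalence of outcomes.** With change defined as pre − post and pre in the model, the group coefficient for change is that for the Month 3 value with the sign reversed. The choice between them does not affect the adjusted inference.

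**The case against.** *The plan does not state a raw change score.* This stands. A reader might infer that the endpoint is fixed as a simple before-minus-after difference. Section 5.3 gives no formula, and the open wording of section 5.2 would permit ANCOVA, percent change or vector analysis. The point is therefore conditional: nothing specifies adjustment, and an unadjusted change is the natural default reading.

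*Preoperative astigmatism need not dominate.* This also stands. A reader might infer that baseline drives most of the variance and that imbalance passes through almost one-for-one. With both SDs at 0.50 D and correlation 0.5, baseline explains 25% of the variance of change and half of an imbalance passes through. The documents give no SD or correlation that would settle which case applies.

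*Validity is not at stake.* Correct: under randomization the unadjusted comparison is unbiased and keeps its 5% level.

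*The secondary endpoint already recovers much of the gain.* This is the strongest objection, and it stands in the favourable cases. In the middle case, unadjusted residual cylinder at Month 3 has SD 0.40 D, a half-width of 0.145 D against 0.138 D adjusted, and power for 0.25 D of 92.4% against 94.5%. At zero correlation the two variances are equal. In the weakest case, however, unadjusted residual cylinder has the same variance as the raw change, so the 25% cut comes entirely from adjustment. A secondary endpoint also does not repair the analysis of the primary one.

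*One value per subject is a simplification.* True: cylinder belongs to an eye and the study is bilateral, so the remedy has to say how the two eyes are handled.

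**Conclusion.** The concern holds in conditional form. The plan has a between-group primary endpoint that is naturally read as a change from baseline, has the baseline refraction in hand, states no stratification by cylinder, and specifies no adjustment. If the change is analysed unadjusted, the comparison is valid but less precise than it could be, and exposed to chance imbalance in preoperative cylinder.

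Under the assumed SDs and correlation, the variance cut available is about 25% to 86%, and a one-standard-error imbalance moves the raw difference by about 0.05 to 0.18 D. That adjustment reduces variance follows from the algebra (a squared term; one degree of freedom is negligible at this sample size). How much it does so depends on inputs that the plan does not give. The change should be made because it is cheap and concerns a primary endpoint; the documents do not support a claim that the planned comparison is invalid.

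**What to change.** In sections 5.2 and 5.3, define the endpoint and its model:

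- **Outcome:** Month 3 refractive cylinder, or its reduction from Visit 1.
- **Model:** treatment group, with the Visit 1 refractive cylinder of the same eye as covariate.
- **Two eyes per subject:** a subject random effect or GEE, or else the subject mean of both eyes for outcome and covariate alike.
- **Reporting:** the adjusted group difference with its 95% CI as the primary result; the raw reduction by group as description only.

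The cost is a few sentences in the plan, slightly more modelling work and one degree of freedom. No new data, visits or subjects are needed.
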